After the participant is in the operating room and before the cesarean delivery, we will use a spirometer to measure forced vital capacity, forced expiratory volume, vital capacity and tidal volume. We will perform these measurements while the participant is in the supine position both before any retraction has occurred and after the traxi device or standard method for panniculus retraction has been applied.

After the cesarean delivery is complete, we will assess provider satisfaction by administering a brief questionnaire developed by our research team. The survey will be distributed to personnel involved in

the delivery either on paper or via REDCap.

We will assess participant satisfaction via a survey that will be available either on paper or via REDCap.

We will conduct a medical record review to collect data on the secondary outcomes below that are not available via spirometry or questionnaire.

Outcomes

The primary outcome will be total operative time, time from incision to closure.

Secondary outcomes will include:

- Spirometry: forced vital capacity, forced expiratory volume, vital capacity and tidal volume
- Provider satisfaction
- Participant satisfaction
- Intraoperative data, such as estimated blood loss and number of scrubbed personnel
- Neonatal outcomes, such as Apgar score and NICU admission
- Length of stay postoperatively,
- Maternal complications, such as need for re-admission and wound disruption or infection.

B. Statistical Considerations

Sample Size Justification: Our sample size calculation is based on data from a prior study that reported total operative time (incision to closure) by BMI [7]. In that study, for patients with a BMI \geq 40 the mean total operative time was 55.0 minutes (±26 minutes). We hypothesize that the operative time in the control arm will be similar to that in the prior study and that the mean operative time in the traxi arm will be 45 minutes (±10 minutes). Using a two-sided alpha of 0.05, in order to achieve 85% power to detect the specified difference we will need 102 participants per arm. To allow for 15% loss to follow-up, we will aim to enroll 120 participants per arm.

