We hypothesize that participants will have a baseline forced vital capacity of 2.0L and that after retraction the forced vital capacity will drop by 0.1L to 1.9L in the control am. Assuming a two-sided alpha of 0.05, we will have more than 85% power to detect a difference between the 0.1L decrease in the control arm and a 0.19 L decrease in the traxi arm (assuming a standard deviation of the difference of 0.2L).

Data Analysis: We will employ an intention-to-treat approach for the data analysis. Descriptive data will be presented as a proportion, mean with standard deviation or median with interquartile range. Comparisons will be made using Chi-square or Fisher's exact test for categorical variables and parametric or non-parametric tests for continuous variables based on data distribution.

We will use linear regression to estimate beta and 95% confidence intervals for difference in the primary outcome, time from incision to closure, between the traxi and control arms. While we anticipate that randomization will balance the distribution of measured and unmeasured potential confounders in the two study arms, if this is not the case, we will assess the influence of potential confounders as needed. We will use a similar analytic approach for the secondary outcomes, which also are continuous. All data will be analyzed with SAS 9.4 (SAS Institute Inc., Cary, NC, USA). All tests will be two sided and a P value <0.05 will be required to confer significance.

Release of Data

Data from study participants enrolled at BWH and MGH will be sent to BIDMC, the coordinating site. A data use agreement will be executed to facilitate data transfer. Data will be sent via secure data transfer.

The PI will create a research steering committee that includes the PI and at least one other coinvestigator. All requests to use data from the study must be made in writing and will be reviewed by the steering committee. Release of data may occur after appropriate data use agreements have been enacted.

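### The plan calls all secondary outcomes continuous and sends them to linear regression, but at least 5 of the 13 named are binary, ordinal or counts, so no suitable effect estimate or interval is specified for the yes/no outcomes

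*Combined protocol and SAP*

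**What the plan says.** The Data Analysis text in section B3.B has two paragraphs that bear on this.

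- The first is general and names no outcome. On summaries: "Descriptive data will be presented as a proportion, mean with standard deviation or median with interquartile range". On tests: "Comparisons will be made using Chi-square or Fisher's exact test for categorical variables", and "parametric or non-parametric tests for continuous variables based on data distribution".
- The second starts with the primary outcome: "We will use linear regression to estimate beta and 95% confidence intervals for difference in the primary outcome, time from incision to closure". It allows confounders to be examined if randomization leaves an imbalance. It then turns to the secondary outcomes: "We will use a similar analytic approach for the secondary outcomes, which also are continuous".

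The Outcomes list in section B3.A includes, among others, "Neonatal outcomes, such as Apgar score and NICU admission", "Length of stay postoperatively" and "Maternal complications, such as need for re-admission and wound disruption or infection". It also lists spirometry, satisfaction of providers and participants, estimated blood loss and the number of scrubbed personnel.

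**The concern.** The sentence on secondary outcomes is the only analysis text that addresses them as a group, and its premise is untrue of several. Taken literally, it classes every secondary outcome as continuous, so none would reach the categorical tests of the preceding paragraph, and the two paragraphs give different instructions for the same variables.

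The categorical provision supplies a test and nothing more. For NICU admission, re-admission and wound complications the plan names no risk difference, risk ratio or odds ratio with an interval, and no model for use if adjustment is wanted. The only estimate, interval and model on offer come from linear regression. These are the safety-type outcomes, where the interval often matters more than the P value. In an open-label trial the choice between the two instructions should be settled before the data are seen.

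**Working it through.** The documents give no figure to reproduce here. The check sets the outcome list against the analysis text, then asks what linear regression does to a yes/no outcome at this sample size.

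**1. Outcome types (section B3.A against section B3.B)**

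| Type | Named secondary outcomes | Number |
|---|---|---|
| Continuous | four spirometry measures, estimated blood loss, length of stay | 6 |
| Yes/no | NICU admission, re-admission, wound disruption/infection | 3 |
| Ordinal | Apgar score | 1 |
| Small count | scrubbed personnel | 1 |
| Scale not given | provider satisfaction, participant satisfaction | 2 |

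Total: 6 + 3 + 1 + 1 + 2 = 13. The firm mismatches are 3 + 1 + 1 = 5.

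**2. Is the test inflated?**

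Inputs: n = 102 per arm and two-sided 0.05, both from section B3.B. Event rates are assumptions, because the documents give none.

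With a 0/1 outcome and an arm indicator, the slope is p2 − p1. The residual variance is s² = n[p1(1 − p1) + p2(1 − p2)]/(2n − 2), SE = √(2s²/n), and t has 2n − 2 = 202 degrees of freedom.

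Example, 0 vs 5 events: p2 = 5/102 = 0.0490; s² = 102 × 0.0490 × 0.9510/202 = 0.0235; SE = √(2 × 0.0235/102) = 0.0215; t = 2.28; P = 0.0235. Uncorrected Chi-square on the same table: 204 × (5 × 102)²/(102 × 102 × 5 × 199) = 5.13, P = 0.0236.

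The same comparison for 1 vs 7 events gives 0.0305 and 0.0305; for 2 vs 9, 0.0301 and 0.0300. The two methods agree to within 0.0001.

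Summing binomial probabilities over all tables with equal rates in both arms gives a type I error for linear regression of 0.014 at a 1% rate, 0.040 at 2%, 0.044 at 5%, 0.052 at 10% and 0.051 at 15%. It is near or below nominal throughout.

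Simulated null mean comparisons at 102 per arm, on assumed distributions, rejected at 0.046 for an Apgar-like score, 0.051 for a personnel-like count and 0.048 for a log-normal length of stay (log SD 0.4).

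**3. Is the interval reliable?**

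Interval: (p2 − p1) ± t(0.975, 202) × SE, with SE as above. Exact coverage is the summed binomial probability of all tables whose interval contains the true difference.

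| Assumed rates | Coverage, 102 per arm |
|---|---|
| 0.5% vs 3% | 93.5% |
| 1% vs 4% | 90.7% |
| 2% vs 8% | about 94% |
| 5% vs 12% | about 95% |

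At 1% vs 4% the interval misses 9.3% of the time. About 8.4 points of that lie on the side where the whole interval sits below the true difference, so the misses mostly understate harm.

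Coverage moves erratically with n because the counts are small. At the enrolment target of 120 per arm, the same sum gives 93.5% for 1% vs 4% and 87.2% for 0.5% vs 3%.

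If neither arm has an event, SE = 0 and the interval has zero width. At a true rate of 1% in both arms this happens with probability 0.99^204 = 0.13.

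**The case against.** The strongest reply is that the plan already covers the yes/no outcomes. The preceding paragraph gives categorical variables a valid test and lets skewed continuous variables, such as length of stay, go to a non-parametric one. The later clause could be read restrictively, as meaning only those secondary outcomes that are continuous, and a similar approach is looser than a fixed assignment. This partly stands: valid unadjusted tests are in the plan. But the comma before the clause makes the restrictive reading strained, and even on that reading no effect measure, interval or adjusted model is named for the yes/no outcomes.

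It is also fair to say that the linear-regression slope on a 0/1 outcome is the risk difference, a legitimate effect measure. The weakness lies in its interval when events are rare.

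Three stronger readings are tempting, and the documents do not support them.

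- A reader might infer that linear regression would produce false positives for complications. It does not: its P values match the uncorrected Chi-square test that the plan itself names, and its type I error is not inflated. A contrast with Fisher's exact test would show only that Fisher is conservative.
- A reader might infer that comparing mean Apgar scores or mean personnel counts is invalid. The mean difference is estimable and its test held close to nominal level. A rank method suits these outcomes better, but that is a matter of suitability.
- A reader might infer that regression breaks down for length of stay. Under moderate skew it did not; heavier tails were not examined.

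**Conclusion.** The point holds as an error of classification with a limited consequence. The statement that the secondary outcomes are continuous is false for 5 of 13 named outcomes and unverifiable for 2 more. It contradicts the paragraph before it, and it leaves three safety-type outcomes with no suitable interval or adjusted model.

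The practical cost is confined to rare events. There, nominal 95% intervals may cover about 91% at 102 per arm (1% vs 4%) and become degenerate when no events occur; at higher unequal rates coverage is about 94% to 95%. These figures rest on assumed event rates, independent participants and ordinary linear-regression standard errors. The primary outcome, its analysis and the sample size are untouched.

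**What to change.** Replace the sentence on secondary outcomes with wording such as:

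> Continuous secondary outcomes (spirometry, estimated blood loss, length of stay) will be analysed by linear regression, or by a non-parametric test if markedly skewed. NICU admission, re-admission and wound disruption/infection will be compared by the Chi-square or Fisher's exact test named above, with a risk difference and risk ratio and 95% confidence intervals by a method suited to small counts (for example a score interval), and by a binary-outcome model if adjusted. Apgar score and number of scrubbed personnel will be compared by a rank test. Satisfaction will be analysed according to its scale.

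The scale and scoring of both satisfaction questionnaires should be stated at the same time, since the last sentence depends on them.

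The cost is wording and a few lines of SAS code, with no new data. Some intervals for rare events will become wider, which is the honest price of better coverage.

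### Every test may confer significance at P<0.05, and no outcome is named to decide Aim 2, which is examined with four overlapping spirometry measures

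*Combined protocol and SAP*

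**What the plan says.** The Outcomes list in section B3.A names one primary outcome: "The primary outcome will be total operative time, time from incision to closure". The secondary outcomes named there come to 13:

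- four lung measures ("Spirometry: forced vital capacity, forced expiratory volume, vital capacity and tidal volume");
- "provider satisfaction" and "participant satisfaction";
- two intraoperative items ("Intraoperative data, such as estimated blood loss and number of scrubbed personnel");
- two neonatal items ("Neonatal outcomes, such as Apgar score and NICU admission");
- postoperative length of stay;
- re-admission, and wound disruption or infection counted as one item.

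The intraoperative, neonatal and maternal lists give examples only, so the number of tests is not fixed.

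Data Analysis in section B3.B plans linear regression with 95% confidence intervals for the primary outcome and a similar approach for the secondary ones. It closes with the rule "All tests will be two sided and a P value <0.05 will be required to confer significance". Nothing ranks the secondary outcomes, adjusts for their number or labels them exploratory.

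Section B1 states three aims. Aim 2 concerns pulmonary function and also mentions oxygen saturation, which the Outcomes list does not name. Among the secondary outcomes, only forced vital capacity has a power statement, beginning "We hypothesize that participants will have a baseline forced vital capacity of 2.0L".

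**The concern.** Operative time answers Aim 1 only. Aims 2 and 3 carry stated hypotheses of their own and rest entirely on secondary outcomes, and the B3.A overview presents the trial as the basis for deciding whether the device belongs in routine practice.

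For Aim 3 the plan lists one participant outcome and one provider outcome, which match the two parts of that hypothesis. For Aim 2 there is no such match. Four related volumes are each tested at P<0.05, and the plan does not say which one settles the question or how a mixed result would be read. If one volume of four is significant, the authors could report a pulmonary effect without departing from the plan, and the reader would have no stated error rate for that claim.

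**Working it through.** **1. The plan's own figure.** Inputs from the sample size section: decreases in forced vital capacity of 0.10 L (control) and 0.19 L (traxi), so a difference of 0.09 L; SD 0.2 L; two-sided alpha 0.05. That sentence gives no sample size, so I assume the trial's 102 evaluable or 120 enrolled per arm.

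Power ≈ Φ(0.09 / (0.2 × √(2/n)) − 1.96)

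- n = 102: Φ(3.214 − 1.960) = 89.5%
- n = 120: Φ(3.486 − 1.960) = 93.6%

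Both agree with the stated power of more than 85%. A two-sided test has the same power for a 0.09 L difference in either direction.

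**2. Four spirometry tests, no true effect.** If the tests were independent, the chance of at least one significant result in either direction is 1 − 0.95^4 = 18.5%. The chance of at least one favouring traxi is 1 − 0.975^4 = 9.6%. Lung volumes in the same patient are correlated. The documents give no correlations, so a range is assumed, using normal test statistics with a common pairwise correlation:

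| Assumed correlation | Any significant volume | At least one favouring traxi |
|---|---|---|
| 0.5 | 15.6% | 7.8% |
| 0.7 | 13.0% | 6.5% |
| 0.9 | 9.4% | 4.7% |
| One test only | 5.0% | 2.5% |

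**3. All 13 named secondary outcomes, no true effect.**

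- Independent, either direction: 1 − 0.95^13 = 48.7%
- Independent, favouring traxi: 1 − 0.975^13 = 28.0%
- Common correlation 0.3 (assumed): about 42% and 21%
- Common correlation 0.5 (assumed): about 33% and 17%

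These give every outcome a full 5% error. NICU admission, re-admission and wound complications are binary, and the plan allows Fisher's exact test. At 102 per arm and assumed event rates of 2%, 5% or 10%, the actual size of that test is about 0.5%, 2.1% or 2.9%. The 13-outcome figures are therefore upper values.

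**4. What the remedies cost in power for forced vital capacity (102 / 120 per arm).**

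- Named as the one deciding Aim 2 outcome at 0.05: 89.5% / 93.6%
- Bonferroni over four volumes (alpha 0.0125): 76.3% / 83.8%
- Bonferroni over 13 outcomes (alpha 0.00385): 62.7% / 72.4%

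**The case against.** The strongest reply is that the plan has one pre-specified primary outcome with its own sample size, and labels everything else secondary. Unadjusted secondary outcomes beside a single primary are largely a matter of reporting. The threshold applies test by test, and regression estimates with confidence intervals are already planned. Much of this stands: the primary test is unaffected, and Aim 3 already has its two outcomes. Neonatal outcomes, length of stay and re-admission serve no stated aim hypothesis, so the 13-outcome total says little about any aim.

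Two stronger readings are tempting, and the documents support neither.

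- A reader might infer that a false claim of benefit is likely. It is not. The 49% counts results in either direction and assumes independence; the figure favouring traxi is at most about 28%. Overlap among the lung volumes lowers the rate.
- A reader might infer that one significant volume is enough to carry Aim 2, or to make the trial positive. The plan never says so. It is silent on what decides Aim 2, and that silence is the point.

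It is also fair to object that naming one outcome per question does not control error across the trial. Four tests at 0.05 (operative time, forced vital capacity, two satisfaction outcomes) give 1 − 0.95^4 = 18.5% if independent. That stands, so the aims should be interpreted separately, with no claim of trial-wide control.

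What the objection does not answer is Aim 2: it has its own hypothesis, four tests, one powered measure and no deciding outcome.

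**Conclusion.** The point holds in a limited form. The primary test keeps its 5% error. For Aim 2, the rule as written gives roughly a 9% to 16% chance of at least one false-positive volume, or about 5% to 8% in favour of traxi, which is roughly two to three times the rate for a single test. This rests on assumed correlations of 0.5 to 0.9 and on no true effect on any volume. Across all 13 secondary outcomes the ceiling is about 49% in either direction and 28% favouring traxi, lower with correlation or sparse binary outcomes. It is an inexpensive improvement to make before analysis and does not threaten the main result.

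**What to change.** Amend Data Analysis in section B3.B as follows.

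- Limit the significance rule to the primary outcome (Aim 1), the between-arm difference in change in forced vital capacity (Aim 2), and the participant and provider satisfaction outcomes (Aim 3, read as two separate hypotheses).
- State that each aim is interpreted separately and that error is not controlled across aims.
- Report all other secondary outcomes, including the other spirometry measures and oxygen saturation, as estimates with 95% confidence intervals, labelled supportive and without significance claims.
- Reconcile the forced vital capacity power statement, which assumes a larger decrease with traxi (0.19 L against 0.1 L), with the Aim 2 hypothesis in section B1 that traxi improves pulmonary function. This is needed before the power statement can justify the choice of deciding outcome.

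The cost is a few sentences, with no added participants or measurements. The downside is that fewer secondary results can be called significant, and that forced vital capacity alone does not cover everything Aim 2 mentions.

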- 6. von Ungern-Sternberg, Effect of obesity and site of surgery on perioperative lung volumes. British Journal of Anaesthesia , Volume 92 , Issue 2 , 202 207.
- 7. https://clinicaltrials.gov/ct2/show/NCT02865083?term=pannus+retraction&rank=1

B3. DESCRIPTION OF RESEARCH PROTOCOL A. Study Design – Overview, Methods, Procedures

Overview

To determine whether the traxi® device warrants incorporation into routine practice, we will conduct an open-label, randomized, controlled trial to evaluate the use of traxi for obese patients undergoing non-urgent cesarean delivery. We will examine operative time, cardiopulmonary function, and patient/provider satisfaction.

Methods

Enrollment/randomization

Screening, recruitment, and enrollment of participants will occur in the obstetrical clinics and on Labor and Delivery at Brigham and Woman's Hospital (BWH), Beth Israel Deaconess Medical Center (BIDMC) and at Massachusetts General Hospital (MGH). Possible eligible patients may be handed a brochure about the study by their OBGYN provider at BIDMC so they can decide make an informed choice about participating. We will review the medical record of potentially eligible patients to confirm eligibility. At the time we approach each patient, we will review the eligibility criteria with the patient to further ensure eligibility. A script is available for the consenter. Specifically, consistent with standard medical care, we will confirm with patients that they do not have a history of allergic reaction to adhesives, such as those used in medical tape.

Participants who meet eligibility criteria and provide written, informed consent will be randomized to the traxi arm or standard of care (control) arm. We will use computer-generated block randomization to randomize participants in a 1:1 ratio to the traxi arm or the control arm. Randomization will be stratified by whether the patient has a history of cesarean delivery / open abdominal surgery versus no history of cesarean delivery / open abdominal surgery versus no history of cesarean delivery.

Study procedures

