Investigators can request to use 1) data that contain elements of a limited dataset or 2) data that are completely de-identified. Investigators who wish to obtain data that contain elements of a limited dataset first must obtain approval from the steering committee and then will have to obtain appropriate approval from the BIDMC Committee on Clinical Investigations (CCI) and from their own institution. After obtaining approval, data may be given to the researchers. Investigators who wish to receive completely de-identified data may do so after approval by the steering committee and after signing a letter indicating that they will not attempt to obtain the identity of any of the participants. A data use agreement or material transfer agreement will be executed as needed.

C. Subject Selection

Inclusion criteria for patients

- Pregnant
- Age 18-50 years
- BMI greater than or equal to 40 kg/m²
- Undergoing non-emergent cesarean delivery
- Able and willing to provide written, informed consent
- Singleton gestation

Inclusion criteria for providers

- Listed as a provider_on the patient's delivery summary
- May include nurse, resident, attending, medical student, anesthesiologist, physician's assistant, surgical technician

Exclusion criteria for patients

- Fetal demise
- Disruption of abdominal skin, such as due to infection, rash, abrasion or laceration
- Known adhesive allergy

B4. POSSIBLE BENEFITS

We do not know whether participants in the study will gain any direct benefit from participation. However, we hope that this study will provide data to inform how we can improve care for future patients. It is possible that participants who are randomized to the intervention arm of this study will have a better delivery experience due to increased preservation of dignity. It also is possible that providers will benefit by improving retraction capability and thus visualization while operating and operative efficiency.

B5. POSSIBLE RISKS AND ANALYSIS OF RISK/BENEFIT RATIO

There are very few anticipated risks involved in this study. Patients with an allergy to adhesives may experience a contact dermatitis allergic reaction to the adhesive of the traxi device or the medical tape.

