Additional risks are largely psychosocial. Obesity can be a difficult topic to navigate with patients. As this device is used only in obese patients, some patients may feel uncomfortable when approached for this study. Study staff will be sensitive to this issue when approaching patients for enrollment.

To protect patient privacy and prevent a breach of confidentiality, all data will be handled in a confidential manner. We will use REDCap, a HIPAA-compliant, web-based data collection tool to securely store all data.

B6. RECRUITMENT AND CONSENT PROCEDURES

Recruitment

At BIDMC and MGH, study staff will review the cesarean delivery schedule and the census on Labor and Delivery to identify patients who may be eligible for the study. To the extent possible, eligibility will be confirmed by reviewing the medical record before the patient is approached. The study staff also will confer with the one of the patient's clinicians to ensure that it is okay to approach the patient about the study. Possibly eligible patients will be handed a brochure by their providers. They may also see the brochure in the OBGYN department and choose to read about it on their own. Patients will be approached on Labor and Delivery in a private space and clinic visits.

In addition, BWH permits study staff to call and email patients for study recruitment. Thus, BWH study staff will approach potentially eligible BWH patients via phone and email, in addition to using the inperson recruitment described above.

Providers who participated in the delivery will be sent an email to ask to participate in a REDCap survey on provider experience. Providers will be identified by looking at the list of providers in the patient's delivery summary.

Consent

Members of the study team will obtain written informed consent from participants when they are in a private clinical space. The participant will be provided with a copy of the informed consent. A script is available for use during enrollment. Providers will be consented in the email communication. The email contains required consent elements so that the providers can be well informed about participation, and they will opt in by responding to the survey.

Subject Protection

We do not believe that pregnant patients are vulnerable. Nonetheless, patients approached will be assured that their participation is completely voluntary and will not affect their clinical care. Participation in the provider survey is voluntary.

B7. STUDY LOCATION

Privacy

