
We will obtain consent in a private clinical setting at the hospital, and surveys will be administered to participants in a private post-partum or OBGYN exam room.

Physical Setting

Study activities will take place at BIDMC, Brigham and Women's Hospital (BWH) and at Massachusetts General Hospital (MGH).

B8. DATA SECURITY

All electronic data will be kept in a restricted-access folder on the BIDMC or MGH secure server, behind the firewall. Any paper resulting from this study will be kept in a locked office belonging to a member of the study staff. We will use REDCap, a HIPAA compliant, web-based collection tool to securely store all data.

B9 Multi-Site Studies

Is the BIDMC PI the lead investigator of the multi-site study? Yes No We are planning to have at minimum a quarterly conference call with the traxi personnel at BWH and MGH to discuss anything about the study. We may have more frequent calls to discuss changes and important updates if necessary. If unanticipated problems, adverse events and/or noncompliance arise, we plan to follow BIDMC/CCI post-approval reportable event guidelines to report these issues. We are working closely with MGH personnel to ensure that they will submit and follow a protocol similar to the one we do. Changes made to the protocol by BWH and MGH must also be approved by us. These amendments can be discussed in conference calls.

B10 Dissemination of Research Results

We will not provide research results directly to participants. Aggregate results will be presented via poster, oral presentation and manuscript.

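### Adhesive skin reaction, the only specific physical risk named in B5, is neither a named outcome nor systematically checked, so its rate by arm could not be reliably estimated

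*Combined protocol and SAP*

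**What the plan says.** The Overview in B3.A gives the purpose of the trial: "To determine whether the traxi® device warrants incorporation into routine practice". The design is open-label.

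B5 states one specific physical risk, and attaches it to both adhesives: "Patients with an allergy to adhesives may experience a contact dermatitis allergic reaction to the adhesive of the traxi device or the medical tape". Of the rest it says "Additional risks are largely psychosocial".

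Among the secondary outcomes in B3.A, the item closest to this risk is "Maternal complications, such as need for re-admission and wound disruption or infection". Skin or adhesive reaction is not named. The source for anything not measured by spirometer or survey is the chart: "We will conduct a medical record review to collect data on the secondary outcomes below that are not available via spirometry or questionnaire". Study procedures describe no skin inspection, no time for one and no grading.

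Two provisions reduce the risk. The patient exclusions in B3.C include "Known adhesive allergy", and under Enrollment/randomization the protocol says "we will confirm with patients that they do not have a history of allergic reaction to adhesives, such as those used in medical tape". Adverse events are covered in B9: "If unanticipated problems, adverse events and/or noncompliance arise, we plan to follow BIDMC/CCI post-approval reportable event guidelines to report these issues".

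**The concern.** A trial meant to decide whether a device should enter routine practice needs a usable rate, in each arm, for the physical harm that its own risk section anticipates. Here that harm has no definition, no assessment time and no assigned source beyond the chart. A mild reaction may never be written down. With three hospitals and no abstraction rule for this item, the sites could also record it differently or not at all. In an open-label trial, unsolicited recording can differ between arms for reasons unrelated to the true rate.

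At stake is the harm side of the benefit–harm summary. The primary outcome, operative time, is unaffected.

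**Working it through.** The plan states no figure on this point, so the check is mainly a reading of sections against each other.

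**Step 1. Trace the risk through the plan.**

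| Element | What the plan provides for adhesive skin reaction |
|---|---|
| Risk (B5) | Named, for the traxi adhesive and for tape |
| Outcome list (B3.A) | Not named; the maternal complications item is open-ended |
| Procedure (B3.A) | Spirometry, provider survey, participant survey, record review; no skin check |
| Analysis (B3.B) | Chi-square or Fisher's exact for categorical variables; no safety analysis by arm |
| Adverse events (B9) | Reported if they arise; not solicited, no comparison by arm |
| Prevention (B3.A, B3.C) | Allergy history asked; known allergy excluded |

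The exclusion removes known reactors. It does not remove a first reaction in someone with no history. For those participants the only routes into the data are a chance chart entry or an adverse event report.

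**Step 2. What systematic collection would give.** B3.B requires 102 participants per arm and plans to enroll 120 (102 / (1 − 0.15) = 120). If every assessed participant in an arm has no reaction, the exact two-sided 95% upper limit p solves (1 − p)^n = 0.025:

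- n = 102: 1 − 0.025^(1/102) = 3.6%
- n = 120: 1 − 0.025^(1/120) = 3.0%

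The two-sided limit matches the plan's two-sided convention. A one-sided 95% limit, 1 − 0.05^(1/102) = 2.9%, would look slightly tighter.

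**Step 3. Chance of seeing any case.** The documents give no reaction rate, so the true rates here are assumptions. P(at least one) = 1 − (1 − p)^n:

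| Assumed rate | n = 102 | n = 120 |
|---|---|---|
| 0.5% | 40% | 45% |
| 1% | 64% | 70% |
| 2% | 87% | 91% |
| 5% | 99.5% | 99.8% |

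**Step 4. Could the arms be compared formally?** Normal-approximation power at two-sided 0.05 is Φ{[|p1 − p2| − 1.96·√(2p̄(1 − p̄)/n)] / √([p1(1 − p1) + p2(1 − p2)]/n)}, where p̄ is the mean of the two rates. For 5% versus 10% with n = 120: (0.05 − 1.96 × 0.0340) / 0.0339 = −0.49, so power is 31%. Other assumed pairs:

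| Assumed rates | n = 102 | n = 120 |
|---|---|---|
| 1% vs 5% | 39% | 44% |
| 5% vs 10% | 27% | 31% |
| 5% vs 15% | 67% | 74% |
| 1% vs 10% | 81% | 87% |

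The approximation is rough at such small counts. The planned size could describe the rate in each arm usefully, but could compare arms only if the difference were large.

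**The case against.** The strongest reply is that harm is not ignored. Wound disruption or infection, re-admission, blood loss, Apgar score, NICU admission and length of stay are all collected, and spirometry after retraction could also show an adverse effect. The wording of the maternal complications item leaves room for a charted skin reaction, and B9 provides a reporting route. B5 ties the reaction to people with an adhesive allergy, and known allergy is both asked about and excluded. The trial is also too small to compare modest differences in reaction rates.

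Much of this stands, and it rules out a stronger reading. A reader might infer that the trial cannot report device harm at all. The documents do not support that, because several harms are collected in both arms. A reader might also infer that reactions would be charted more readily for the new device than for tape, producing a false excess. Unequal recording is possible in an open-label trial, but the documents give no charting rates, so neither its direction nor its size can be stated.

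The reply does not close the narrower gap. An open list permits skin reaction to be abstracted without requiring it. Reactive reporting does not solicit events from every participant, so it gives no dependable rate. None of the listed outcomes measures the reaction that B5 names. Limited power argues against a formal test, not against recording the event.

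**Conclusion.** The point holds in a limited form. New skin reaction at the retraction site is not prespecified and not systematically ascertained, so its rate by arm could not be reliably estimated from the trial as planned. What is lost is a descriptive safety statement: with no events among 102 to 120 assessed participants, an upper limit of 3.6% to 3.0% per arm. Those limits assume that every counted participant was actually assessed.

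The true rate is unknown and may be low after the allergy exclusion. The conclusion does not depend on it, nor on any assumption about which arm would be recorded more fully. Adding the item is worthwhile because the trial is meant to inform routine use; leaving it out does not threaten the primary result.

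**What to change.** Add to the secondary outcomes in B3.A a named safety outcome: *skin reaction or skin injury at the retraction site (none / erythema / blister or skin tear / needing treatment)*.

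- **Collection.** Use one identical item in both arms, whatever retraction method was used, since B3.A describes the control only as the standard method and tape cannot be assumed for everyone.
- **Timing.** Attach it to the existing participant survey and state a time window. Neither Study procedures in B3.A nor the survey setting in B7 fixes when the survey is given. State also who completes the item.
- **Reporting.** Give counts by arm and grade, the number assessed, and exact two-sided 95% confidence intervals. Label the result descriptive, with no powered comparison.

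The cost is one extra data item per participant and a fixed survey window. Assessment remains unblinded, and a single time point can miss reactions that resolve before it or appear after it. Allocation, sample size and the primary analysis do not change.
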